**Table 6.7: HER3ECD Sampling Time Points** 

Cycle	Day	Sampling Time Point (Acceptable Range)
Screening (Dose Escalation and Dose Finding Parts Only)	-	Latest data within 7 days prior to enrollment
Cycle 1 (Dose Expansion Part Only)	Day 1	BI (– 8 hours)
Cycle 2 (Dose Expansion Part Only, if optional tumor biopsy is obtained)	Day 3	±4 hours from time of biopsy, if obtained
EOT (Dose Expansion Part Only)	-	The date Investigator decides the discontinuation of the study treatment (+ 7 days)

EOT = end of treatment; BI = before infusion.

Refer to the Laboratory Manual for information regarding the handling and shipping of blood samples.

Blood samples of approximately 10 mL for cfDNA analyses and 10 mL for cfRNA analyses will be collected at the time points specified in Table 6.8.

Table 6.8: cfDNA and cfRNA Sampling Time Points

Cycle	Day	Sampling Time Point (Acceptable Range)
Cycle 1 (Dose Expansion Part Only)	Day 1	BI (- 8 hours)
Cycle 2 (Dose Expansion Part Only, if optional tumor biopsy is obtained)	Day 3	± 4 hours from time of optional biopsy, if obtained
EOT (Dose Expansion Part Only)	-	The date Investigator decides the discontinuation of the study treatment (+ 7 days)

EOT = end of treatment; BI = before infusion.

Refer to the Laboratory Manual for information regarding the handling and shipping of whole blood samples.

Blood samples of approximately 4 mL for cTnI analyses will be collected at the time points specified in Table 6.9.

**Table 6.9: cTnI Sampling Time Points** 

Cycle	Day	Sampling Time Point (Acceptable Range)
Screening	-	Latest data within 7 days prior to enrollment
At every cycle	Day 1	3 hours after EOI (± 1 hour)
ЕОТ	-	The date Investigator decides the discontinuation of the study treatment (+ 7 days)

EOI = end of infusion; EOT = end of treatment.

Refer to the Laboratory Manual for information regarding handling and shipping of serum samples.

Exploratory biomarker (HER3ECD, cfDNA, cfRNA) samples will not be collected after the implementation of protocol Version 8.0, which occurs upon the IRB approval of protocol Version 8.0 at study sites.

# 6.10.6. Anti-Drug Antibodies

Blood samples for ADA of approximately 4 mL analyses will be collected at the time points specified in Table 6.10. Serum concentrations of U3-1402 and/or total anti-HER3 antibody may be measured using the same ADA samples for purpose of anti-drug antibody assessment.

Refer to the Laboratory Manual for information regarding the handling and shipping of serum samples.

**Table 6.10: ADA Sampling Time Points** 

Cycle	Day	Sampling Time Point (Acceptable Range)
Cycle 1	Day 1	BI (– 8 hours)
	Day 8	7 days after infusion (± 1 day)
Cycle 2	Day 1	BI (– 8 hours)
After Cycle 4 at every 2 cycles (eg, Cycle 4, 6, 8, 10, 12)	Day 1	BI (– 8 hours)
ЕОТ	-	The date Investigator decides the discontinuation of the study treatment (+ 7 days)
F/U visit a	-	28 days (- 7 days) after the last study drug administration or until starting new anticancer treatment, whichever comes first

BI = before infusion; EOT = end of treatment; F/U = follow up.

<sup>a For subjects with positive ADA at F/U visit, additional serum ADA samples may be collected every 3 months (± 1 month) up to 1 year from the last dose of study drug, or if the ADA becomes negative, or if ADA titer becomes less than baseline (applicable when pre-existing ADA is observed), or if the subject starts another therapy for cancer, or withdraws consent from the study, whichever occurs first.

## 7. PHARMACOKINETIC/PHARMACODYNAMIC ASSESSMENTS

## 7.1. Pharmacokinetic Assessment(s)

The serum PK parameters listed in Table 7.1 of U3-1402, total anti-HER3 antibody and MAAA-1181a for each subject will be estimated using standard noncompartmental methods. The other PK parameters (elimination rate constant associated with the terminal phase [Kel], T1/2, CL, volume of distribution based on the terminal phase [Vz], and Vss) will be calculated if data permits. Population PK and exposure-response analyses for U3-1402, total anti-HER3 antibody and MAAA-1181a will be performed to characterize the relationships between dose and exposure and between exposure and efficacy and/or safety endpoints. If performed, results of population PK or exposure-response analyses will be reported separately (ie, not in the Clinical Study Report).

Table 7.1: Pharmacokinetic Parameters

Analyte	PK parameters
U3-1402, total anti-HER3 antibody and MAAA-1181a	AUClast, AUCtau, Cmax, Tmax, Ctrough

## 7.2. Pharmacodynamic Assessment(s)

Not applicable.

## 7.3. Biomarker and Exploratory Assessment(s)

Subjects will be requested to provide a tumor sample for assessing HER3 expression at study entry and optionally at some additional time points during the course of clinical study.

Clinical samples, including tumor tissue and blood, will be retained until the end of the defined storage period and may be analyzed for exploratory research purposes. The sample collection information should be recorded in the eCRF.

Detailed instructions for the collection, handling, and shipping of biomarker samples are outlined in the Laboratory Manual.

All subjects will be asked to provide written consent to supply tumor tissue (archival tissue or fresh tumor biopsy) and blood samples for research purposes prior to study entry.

## 7.3.1. HER3 expression

The level of HER3 expression will be assessed by IHC using archival or fresh biopsy provided by the patient. In the Dose Expansion Part, the level of HER3 expression in pre-study treatment, on-study treatment and post-study treatment will be assessed with the biopsy sample.

#### 7.3.1.1. Tumor Sample Collection

Refer to the Laboratory Manual for instructions regarding archived and fresh tumor tissue handling and shipping.

#### Study Entry

Tissue to analyze for HER3 expression for study eligibility may be obtained from fresh tumor biopsy or from archived tumor samples.

A fresh tumor biopsy may be requested from subjects with a HER3-negative tissue
result that was assayed using an archived tumor tissue sample. Tumor tissue obtained
from this fresh biopsy should be sent to the central laboratory for the re-assay of the
HER3 status. Tumor samples must be obtained after the date of informed consent for
tumor screening.

#### Pre-treatment Biopsy

- For the Dose Finding Part, perform an **optional** tumor biopsy for subjects with HER3-positive tissue that was assayed using an archived tumor tissue sample. Tumor tissue from the fresh biopsy should be sent to the central laboratory for analysis of HER3 IHC; these results are not required for study entry.
- For the Dose Expansion Part, perform a tumor biopsy for subjects with HER3-positive tumor tissue that was assayed using an archived tumor tissue sample. Tumor tissue from this fresh biopsy should be sent to the central laboratory for analysis of HER3 IHC; these results are not required for study entry.

#### On-study Biopsy (Dose Expansion Part Only)

An **optional** on-study tumor biopsy may be performed approximately 48 to 72 hours after the end of the U3-1402 infusion on Cycle 2, Day 1. Additionally, blood for HER3ECD, cfDNA, cfRNA, and PK should be collected ± 4 hours from the time of this optional biopsy, if obtained. A minimum of 20 subjects in the HER3-high, HR-positive cohorts, a minimum of 6 subjects in the HER3-low, HR-positive cohort, and a minimum of 9 subjects in the HER3-high, TNBC cohort will be required to submit on-treatment biopsies during the Dose Expansion Part. Consent for this biopsy should be documented in the tissue consent portion of the ICF. Tumor tissue from this biopsy should be obtained from the primary tumor or metastatic site.

#### End-of-treatment Biopsy (Dose Expansion Part Only)

An **optional** end-of-treatment tumor biopsy may be performed at the time of progression or discontinuation from study treatment. Consent for this biopsy should be documented in the tissue consent portion of the appropriate ICF. Tumor biopsy should be obtained from the primary tumor or a metastatic site, preferably from a site of recent radiographic progression, within 30 days of the date of discontinuation, and prior to starting any new anticancer treatment.

Any SAEs directly related to a tumor biopsy procedure and performed after signing the appropriate ICF should be reported according to Section 8.5.

#### 7.3.2. Biomarker Assessments in Tumor Tissue and Blood Samples

The biomarkers will be analyzed with the intent of identifying those subjects who will most likely derive clinical benefit from treatment with U3-1402. Further exploratory tissue or blood-based biomarkers may be analyzed based on emerging scientific knowledge to better understand the target disease and also possibly the effects of study treatment.

Exploratory analysis will be done to assess the status of some biomarkers (eg, HER3ECD, mRNA, cfDNA, cfRNA, PD-L1 and cTnI).

During the study, in addition to the biomarkers specified above, other exploratory biomarker research may be conducted on tissue and/or blood samples. These studies would extend the search for other potential biomarkers relevant to the effects of U3-1402, cancer, and/or resistance to the treatment. This may include the development of ways to detect, monitor or treat cancer. These additional investigations would be dependent upon clinical outcome, reagent and sample availability.

The results from exploratory biomarker research may be pooled with biomarker data from other studies with the investigational product to generate hypotheses to be verified in future studies.

## 7.4. Immunogenicity

Blood samples will be obtained at the time points specified in Section 17.1. The details on immunogenicity blood sample collection, handling and shipment are described in the Laboratory Manual. The immunogenicity testing will be performed using a validated anti-drug antibodies (ADA) assay which is comprised of tiered steps including screening, confirmatory as well as titer determination. ADA samples confirmed positive will be banked until availability of a neutralizing anti-drug antibody assay.

Immunogenicity will be assessed through characterization of incidence and titer of ADA. The number and percentage of subjects will be calculated for the presence or absence of development of ADA after the start of administration, defining subjects who are negative for ADA at all time points as negative and subjects who are positive for ADA at least 1 time point as positive. The raw values and change from baseline for ADA titers will be summarized by time point and treatment group using descriptive statistics.

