### 2.1.2.2. Dose Finding and Dose Expansion Parts

The secondary objective is as follows:

- 1. To assess the PK profiles of U3-1402, total anti-HER3 antibody, and MAAA-1181a.
- 2. To assess the incidence of ADA against U3-1402.

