## 3.1.1.4. Duration of Subject Participation

The number of treatment cycles is not limited in this study. Subjects will continue study treatment until withdrawal of consent, progressive disease (PD), unacceptable toxicity, death, or termination of the study by Sponsor.

There is an end-of-treatment (EOT) Visit which occurs within 7 days after the date of discontinuation. A 28-Day F/U Visit (- 7 days) takes place 28 days after the last U3-1402 administration. If the subject begins another anticancer therapy before the end of the 28 days (- 7 days), every effort will be made to complete all of the F/U assessments prior to starting the new therapy. For further details concerning assessments performed at the EOT and F/U Visits refer to Section 6.7 and Section 6.8, respectively.

For subjects with positive ADA at F/U visit (or EOT visit if F/U visit was not performed), additional serum ADA samples should be collected every 3 months (± 1 month) for up to 1 year after the last dose of U3-1402, unless one of the following occurs sooner; the ADA becomes negative; the ADA titer falls below baseline if ADA was measurable prior to first dose of U3-1402; the subject starts another therapy for cancer; or the subject withdraws consent from the study.

After discontinuation from study treatment, follow-up information for survival and subsequent anticancer therapy, if available, should be collected approximately every 3 months; refer to Section 6.9 for details.

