# Within 8 hours prior to infusion

- Perform a 12-lead ECG in triplicate as indicated in Table 6.1.
- Obtain PK blood sample as indicated (Section 6.10.3).
- Obtain blood sample for ADA (Section 6.10.6).
- [Dose Expansion Part Only] Obtain blood samples for HER3ECD, cell-free DNA (cfDNA), and cell-free RNA (cfRNA) (Section 6.10.5).

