#### 11. STATISTICAL METHODS

#### 11.1. General Statistical Considerations

The primary analysis is to assess the efficacy, safety, and tolerability of U3-1402 in subjects with HER3-positive metastatic breast cancer and to determine the MTD/RDE or establish the safety and tolerability of the maximum administered dose of U3-1402.

The data cutoff for the primary analysis will occur after all subjects have either discontinued the study or have been followed for at least 9 months following the first dose of study treatment, whichever is earlier. The primary analysis data cutoff may be extended if emerging data show responses are occurring later. The final analysis of the study will occur after all subjects have discontinued from the study. Data collected beyond the primary analysis cut-off time point will be presented as appropriate in a Clinical Study Report (CSR) addendum.

The data analyses will also be conducted during the Dose Escalation and Dose Finding Parts.

Descriptive statistics will be provided for selected demographic, safety, and PK data by cohort and time as appropriate. Descriptive statistics on continuous data will include means, medians, standard deviations, and ranges (as well as geometric means and geometric coefficient of variation for Cmax and AUC PK parameters), while categorical data will be summarized using frequency counts and percentages. Graphical summaries of the data may be presented.

Assessments of change from baseline to post-treatment or the ratio of post-treatment to baseline will include only those subjects with both baseline and post-treatment measurements. The last nonmissing value of a variable taken before the first dose of study drug will be used as the baseline value, unless otherwise specified. In general, missing or dropout data will not be imputed for the purpose of data analysis, unless otherwise specified.

Safety analyses will be performed based on the safety analysis set. Analysis of PK parameters will be based on the PK analysis set and biomarker analyses will be based on the Full Analysis Set (FAS). Efficacy endpoints will be analyzed based on the FAS. Data will be summarized by cohort, RDE cohort(s) (Dose Escalation and Dose Finding Parts), and overall.

A detailed Statistical Analysis Plan (SAP) describing the methodology to be used in the final analysis will be prepared and finalized before database lock. Statistical methods described within this document may be changed based on advances in research.

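### The ADA incidence rule in Section 7.4 ignores baseline status, so subjects with pre-existing ADA can be counted as having developed it on treatment

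*Combined protocol and SAP*

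**What the plan says.** ADA incidence is a secondary objective in all three parts of the study. For the Dose Finding and Dose Expansion Parts, Section 2.1.2.2 reads "To assess the incidence of ADA against U3-1402", and Section 2.1.2.1 has the equivalent for Dose Escalation.

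Section 7.4 gives the planned summary. It is a number and percentage of subjects for the "presence or absence of development of ADA after the start of administration". A subject negative throughout is negative; the other half of the rule classes "subjects who are positive for ADA at least 1 time point as positive". The same section plans a separate descriptive summary of titers, as raw values and as change from baseline.

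On timing, Section 7.4 states: "Blood samples will be obtained at the time points specified in Section 17.1". The Section 17.1 tables list two ADA samples in Cycle 1. Table 6.10 identifies them as one before infusion on Day 1 and one on Day 8. The pre-infusion list in Section 6.4.4 confirms the first.

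Pre-existing ADA is provided for in the follow-up rules. Section 3.1.1.4 ends extended ADA sampling when "the ADA titer falls below baseline if ADA was measurable prior to first dose of U3-1402". The Table 6.10 footnote has a similar condition, "ADA titer becomes less than baseline (applicable when pre-existing ADA is observed", and Section 6.8 repeats it.

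**The concern.** The label and the rule describe different quantities. The label is treatment-emergent: antibody that appears once dosing has begun. The rule is ever-positive: any positive result, whatever the subject's status before the first infusion.

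The planned percentage is the summary for this secondary objective. If some subjects enter with pre-existing ADA, it attributes to U3-1402 antibody that was present before any U3-1402 was given. Where true treatment-emergent incidence is low, a handful of baseline positives could make up most of the reported figure. The rule can also be read in two ways, which may give different counts from the same data.

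**Working it through.** The plan states no ADA rate, so there is no figure to reproduce. The check has two parts: what the rule does to each type of subject, and the size of the error under stated assumptions.

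**Types of subject**

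| Pre-dose result | Post-dose results | Treatment-emergent? | Rule over all samples | Rule over post-dose samples only |
|---|---|---|---|---|
| Negative | All negative | No | Negative | Negative |
| Negative | At least 1 positive | Yes | Positive | Positive |
| Positive | All negative | No | **Positive** | Negative |
| Positive | Positive, no titer rise | No | **Positive** | **Positive** |
| Positive | Positive, titer boosted | Yes | Positive | Positive |

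The bold cells are misclassified. Restricting the rule to post-dose samples corrects the third row but not the fourth.

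**Size**

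All four inputs are assumptions; none is in the documents.

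- b: share of subjects ADA-positive at baseline
- t: rate of post-dose positivity in baseline-negative subjects
- k: share of baseline positives who are truly boosted
- p: share of baseline positives still positive after dosing, with p at least k

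Each subject is taken to have a baseline and at least one post-dose result.

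- Treatment-emergent rate = (1−b)t + bk
- All-samples rule = b + (1−b)t, an excess of b(1−k)
- Post-dose rule = bp + (1−b)t, an excess of b(p−k), which is never larger than the all-samples excess

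For b = 5% and t = 3%, (1−b)t = 0.95 × 3% = 2.85%.

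- All-samples rule: 5% + 2.85% = 7.85%
- Treatment-emergent, k = 0: 2.85%, so the excess is 5.0 points
- Treatment-emergent, k = 50%: 2.85% + 2.5% = 5.35%, so the excess is 2.5 points
- Post-dose rule, p = 50%: 2.5% + 2.85% = 5.35%, an excess of 2.5 points at k = 0 and none at k = 50%
- Post-dose rule, p = 100%: 7.85%, the same as the all-samples rule

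The excess does not depend on t. For the all-samples rule over a range of b, with counts in about 110 Dose Expansion subjects (Section 3.1.5):

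| b | Excess, k = 0 | Excess, k = 50% | Subjects of 110, k = 0 | Subjects of 110, k = 50% |
|---|---|---|---|---|
| 0 | 0 | 0 | 0 | 0 |
| 2% | 2.0 points | 1.0 point | 2.2 | 1.1 |
| 5% | 5.0 points | 2.5 points | 5.5 | 2.75 |
| 10% | 10.0 points | 5.0 points | 11.0 | 5.5 |

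If results are shown by cohort, the counts are small. At b = 5% and k = 0 the excess is 30 × 5% = 1.5 subjects in a cohort of 30, and 20 × 5% = 1 in the HER3-low cohort of 20.

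**Whether another section repairs it**

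Section 11.1 defines baseline generally: "The last nonmissing value of a variable taken before the first dose of study drug will be used as the baseline value". Section 7.4 does not apply that definition to the positive/negative classification. Section 11 has no ADA derivation, and the change-from-baseline titer summary does not reclassify any subject.

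**The case against.** The strongest reply is that the all-samples reading is strained. The rule hangs on a phrase about development after dosing starts, and a sample drawn before the first infusion cannot show that. Section 17.1 is a table of blood volumes and frequencies rather than an analysis window. On the more natural post-dose reading the excess is b(p−k), so the table above is an upper bound, reached only if every baseline positive stays positive. This is fair as to size. It does not remove the error, because unboosted baseline positives who remain positive are still counted.

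Second, the size is wholly assumed. The follow-up rules are conditional: they show that the protocol allows for pre-existing ADA, not that any subject has it. This stands, and the effect may be nil.

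Third, the planned titer summaries would let a careful reader see pre-existing and unboosted ADA. They lessen the risk of a misleading conclusion but leave the percentage as it is.

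Fourth, Section 11.6 defers detailed methods to a SAP, which might define ADA incidence properly. No such derivation appears in the text reviewed. If one exists, Section 7.4 would still need to agree with it.

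Fifth, the objectives say incidence of ADA, not treatment-emergent ADA, so relabelling the count or adding a baseline column would cure the mismatch. That would remove the mislabelling. It would not deliver the quantity that Section 7.4 says it will report.

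**Conclusion.** The concern holds. As written, the Section 7.4 rule does not measure what its label describes, and this is so on either reading of the time points. It is an error in a stated rule, not merely missing detail.

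The excess is b(1−k) if all samples count and b(p−k) if only post-dose samples do. For assumed baseline prevalences of 0 to 10% and no boosting, the first runs from 0 to 10 percentage points; the second is the same or smaller. Those figures rest on assumed inputs.

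The consequence is limited to a descriptive secondary summary; no hypothesis test or dose decision uses it. The rule should be corrected before database lock.

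**What to change.** Amend the classification in Section 7.4 and put the same derivation in the SAP:

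- Take the pre-dose Cycle 1 Day 1 sample as baseline, using the Section 11.1 definition.
- Count a subject as treatment-emergent if baseline is negative with at least one positive post-dose result, or if baseline is positive and a post-dose titer exceeds it by a pre-specified margin larger than assay variability.
- Use as denominator the subjects with a baseline and at least one post-dose result.
- Report baseline prevalence separately, so that pre-existing ADA remains visible.

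The cost is a wording change in Section 7.4 and one SAP derivation. The pre-dose sample and titer determination are already planned, so no extra blood is drawn. The titer margin has to be chosen and justified in advance, and subjects lacking a baseline or post-dose result leave the denominator.

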## 7.5. Pharmacogenomic Analysis

## 7.5.1. Genomic or Genetic Banking and Analysis

## 7.5.1.1. Genomic or Genetic Banking and Analysis

In the Dose Expansion Part, a single blood sample (20 mL) for cfDNA (10 mL) and cfRNA (10 mL) analysis will be collected pretreatment on Cycle 1, Day 1; on treatment Cycle 2, Day 3; and at EOT from subjects who provide consent.

Pharmacogenomic samples may be analyzed for genes involved in absorption, distribution, metabolism, elimination, safety, and efficacy of the study drug. Additionally, samples may be analyzed for genes involved in study drug-related signaling pathways, or to examine diseases or physiologic processes related to the study drug. Subject samples will not be sold to anyone. This information may be useful in increasing the knowledge of differences among individuals in the way they respond to the study drug, as well as helping in the development of new drugs or improvement of existing drugs.

